**Research on the Construction of a Prognostic Model for COPD
Complicated with Sarcopenic Obesity Based on Bioelectrical
Impedance Phase Angle Technology (COSAT)**

Research Protocol

Main researchers: [name], [name]

Clinical research department: Respiratory and Critical Care

Medicine Sponsor: [name]

Ethics Review No.:2025K200

Scheme Version No: 01

Plan Preparation date: July 15th, 2025

Research Objectives:

This study aims to explore the diagnosis, impact, and prognostic factors of COPD complicated with sarcopenic obesity using multi-segment bioelectrical impedance phase angle technology. It seeks to clarify the diagnostic value and efficacy of body composition analysis in specific populations, analyze the relationship between phase angle and COPD severity as well as quality of life, investigate its predictive role for adverse outcomes, and reveal the effects of inflammation and metabolic disorders in sarcopenic obesity. The goal is to provide a basis for early screening and precise intervention to improve patient prognosis.

Proposed Research Methods

Inclusion Criteria

- (1) Age over 65 years;**
- (2) Ability to complete physical activity assessments and pulmonary function tests;**
- (3) Complete medical records, willingness to adhere to follow-up arrangements, and provision of adverse event reports via telephone or outpatient visits, with signed informed consent;**
- (4) COPD diagnosis based on the American Thoracic Society (ATS)/European Respiratory Society (ERS) GOLD definition, with a post-bronchodilator FEV1/FVC ratio < 0.70, current or former smokers with a smoking history of ≥ 10 pack-years.**

Exclusion Criteria:

- (1) Severe cognitive impairment or hand deformities (e.g., rheumatoid arthritis) preventing body composition measurements;**
- (2) Incomplete clinical or follow-up data or unwillingness/inability to undergo regular follow-up;**
- (3) Severe systemic edema;**
- (4) Presence of cardiac pacemakers or significant metal implants that may interfere with measurements;**
- (5) Voluntary withdrawal for any reason, including loss to follow-up.**

Data Collection:

Demographic and clinical data: Gender, smoking status (never, former, current), age, height, weight, waist circumference, BMI, skeletal muscle index (SMI), body fat content,

visceral fat index, and segmental phase angles measured via bioelectrical impedance analysis.

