Clinical records: Smoking history, comorbidities (Charlson Comorbidity Index), nutritional status (MNA-SF), physical performance (SPPB), medication use, pulmonary function tests, COPD exacerbations in the past year, CAT score, mMRC score, and St. George's Respiratory Questionnaire (SGRQ).

Laboratory tests: Blood samples for CBC, CRP, cholesterol, albumin, HbA1c, IL-6, and TNF- α (ELISA).

Sample Size Calculation:

Using PASS 15.0 for repeated-measures ANOVA ($\alpha = 0.05$, power = 90%), with a COPD prevalence of 15% and a 2:1 ratio for sarcopenic obesity vs. non-sarcopenic groups, the study requires 200 participants (33 sarcopenic obese, 33 non-obese sarcopenic, 72 obese non-sarcopenic, and 72 non-obese non-sarcopenic).

Diagnostic Criteria:

Sarcopenia: Asian Working Group criteria: SMI (InBody S10) $<7.0 \text{ kg/m}^2$ (men) or $<5.7 \text{ kg/m}^2$ (women); grip strength $<28 \text{ kg}$ (men) or $<18 \text{ kg}$ (women); gait speed $<0.8 \text{ m/s}$. **Obesity:** BMI $\geq 28 \text{ kg/m}^2$ or waist circumference $\geq 85 \text{ cm}$ (men)/ $\geq 80 \text{ cm}$ (women); body fat $\geq 24.3\%$ (men) or $\geq 33.2\%$ (women).

sarcopenic Obesity: Coexistence of sarcopenia and obesity.

Assessments:

Physical Performance: Short Physical Performance Battery (SPPB: balance, gait speed, chair stands; score 0–12).

Nutritional Status: Mini Nutritional Assessment (MNA-SF; score 0–12).

Phase Angle: Measured via InBody S10 at six frequencies (1kHz–1000kHz) across five body segments, calculated using resistance (R) and reactance (Xc):

$\text{PHA} = \arctan((\text{Xc_right arm} + \text{Xc_trunk} + \text{Xc_right leg}) / (\text{R_right arm} + \text{R_trunk} + \text{R_right leg})) \times 180^\circ / \pi$.

Follow-up Endpoints:

Primary: Changes in pulmonary function, dyspnea scores, and body composition at 2 years.

Secondary: Acute exacerbations, hospitalizations, or death within 2 years. Follow-ups at 6, 12, and 24 months.

Grouping patients based on whether they have sarcopenic obesity, the differences in clinical data between the two groups were analyzed. Statistical analysis was performed using SPSS 24.0 statistical software.

Analysis of Demographic Characteristics and Clinical Data:

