The age and gender distribution of the patients were described. Based on whether the patients had sarcopenic obesity, they were divided into two groups. The differences in clinical data between the two groups, including age distribution, smoking status, obesity-related body fat, pulmonary function, whole-body and segmental phase angle, were analyzed. Continuous variables were expressed as mean \pm standard deviation, and categorical variables were expressed as percentages. Differences between groups were analyzed using Student's t-test for continuous variables and the chi-square test for categorical variables, depending on the data type.

Analysis of Factors Associated with COPD Complicated by Sarcopenic Obesity:

Univariate and multivariate analyses were conducted on data from COPD patients with sarcopenic obesity. Using clinical data variables, nutritional status, physical activity capacity, whole-body and segmental phase angle, logistic regression was applied to analyze the factors associated with sarcopenic obesity in COPD patients.

Analysis of the Prognostic Predictive Value of Sarcopenic Obesity in Obstructive Pulmonary Disease:

The differences in hospital stay length, acute exacerbation readmission rate, and mortality between COPD patients with sarcopenic obesity and those without sarcopenia at baseline were compared. Kaplan-Meier analysis was used for statistical analysis, and differences were expressed using the log-rank test.

COSAT study

INFORMED CONSENT FORM

This document provides you with information to help you decide whether to participate in this clinical research study. Please read it carefully. If you have any questions, please direct them to the researcher in charge of this study.

Your participation in this study is voluntary. This research has been reviewed and approved by the institutional ethics review committee of our research institution.

The background, objectives, research process, and other important information are as follows:

Research Purpose:

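### Of the three declared secondary endpoints only death is analysed as declared; exacerbations and hospitalizations are replaced by stay length and readmission, which have no defined population or time origin

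*Combined protocol and SAP*

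**What the plan says.** Under Follow-up Endpoints the combined protocol and SAP lists "Secondary: Acute exacerbations, hospitalizations, or death within 2 years" and sets the contact schedule: "Follow-ups at 6, 12, and 24 months".

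The prognostic section names the outcomes to be compared as "The differences in hospital stay length, acute exacerbation readmission rate, and mortality", taken "between COPD patients with sarcopenic obesity and those without sarcopenia at baseline were compared". One method serves all of them: "Kaplan-Meier analysis was used for statistical analysis, and differences were expressed using the log-rank test".

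Elsewhere exacerbations appear only as baseline history, among the clinical records: "COPD exacerbations in the past year". The inclusion criteria do not require a hospital admission. They do require willingness to be followed up, including "provision of adverse event reports via telephone or outpatient visits, with signed informed consent".

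**The concern.** The endpoint list and the analysis section should name the same outcomes, and they do not. If the analysis section is followed as written, exacerbations treated without admission have no follow-up analysis, and neither does first or all-cause hospitalization. Stay length and readmission enter as outcomes although nobody declared them.

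The substitutes are also incompletely defined. A readmission presupposes an earlier admission, and a length of stay presupposes an admission. The plan does not say how a patient who is never admitted contributes to either, or when the clock starts. If such patients drop out of the comparison, the groups are no longer the baseline groups: they are subsets selected by a later event that sarcopenic obesity may itself influence.

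The title promises a prognostic model, and this is the section that would support a prognostic claim. If the outcome definitions stay open, two analysts could report different results from the same text, and the choice could be made after the data are seen.

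**Working it through.** The check is mainly a comparison of the two sections.

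**Declared endpoint against analysis**

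| Declared (Follow-up Endpoints) | What the prognostic section does |
|---|---|
| Acute exacerbations | Only those leading to readmission |
| Hospitalizations | Not as an event; stay length, and readmission for exacerbation only |
| Death | Mortality, as declared |

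Analysed as declared: 1 of 3.

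**Analysed outcome against declaration**

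| Analysed | Declared endpoint? | Depends on admission as worded? |
|---|---|---|
| Stay length | No | Yes |
| Exacerbation readmission | No | Yes |
| Mortality | Yes (death) | No |

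Undeclared: 2 of 3.

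**Time origin and risk set.** Kaplan-Meier and the log-rank test need a start time, an event and a censoring rule. For mortality, baseline to death within 2 years is the natural reading. For readmission, the start could be discharge from an index admission, which eligibility does not supply, or the baseline visit, in which case the event is simply an admission. For stay length, the curve could run from admission to discharge, which exists only for admitted patients; the plan describes no version that includes the others. The text does not choose between these.

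**Design figures.** The plan gives no effect size, event rate or power for this analysis, so there is no figure to reproduce. The planned groups come from the sample size statement: "the study requires 200 participants (33 sarcopenic obese, 33 non-obese sarcopenic, 72 obese non-sarcopenic, and 72 non-obese non-sarcopenic". The comparison is therefore 33 against 72 + 72 = 144, or 177 patients. (The four counts sum to 33 + 33 + 72 + 72 = 210, not 200; that is a separate matter and does not bear on this point.)

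**Loss of information, illustration only.** The hazard ratios and event proportions below are assumptions; none is in the documents. Schoenfeld's approximation at two-sided 5% is

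power = Φ(√(d·p·(1−p)) × ln HR − 1.96), with p = 33/177 = 0.186 and p(1−p) = 0.152.

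With HR = 1.8 (ln HR = 0.588):

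- 60% with an event: d = 0.60 × 177 = 106.2; Φ(2.36 − 1.96) = 66%.
- 30% with an event: d = 53.1; Φ(1.67 − 1.96) = 39%.
- 20% with an event: d = 35.4; Φ(1.36 − 1.96) = 27%.

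So if any exacerbation occurred in 60% of patients and an exacerbation admission in 20–30%, power at the same hazard ratio would fall from 66% to 27–39%. The result depends on that common hazard ratio: with HR = 2.5 for admissions, 53.1 events give Φ(2.60 − 1.96) = 74%, above the 66%. All that holds without assumptions is that patients with any exacerbation cannot be fewer than those admitted for one. The calculation also treats all 177 as at risk, so it says nothing about selection bias.

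**The case against.** The strongest reply is that the two sections differ in wording more than in substance. The groups are fixed at baseline, and no sentence limits the comparison to admitted patients. Kaplan-Meier can keep never-admitted patients in the risk set as censored, stay length can be set to zero days for them, and readmission may loosely mean any admission for an exacerbation. The "or" in the endpoint statement may denote a composite.

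This has force against four stronger readings that a reader might infer:

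- *That exacerbations are never analysed.* Those leading to readmission are; what is missing is an analysis of all of them.
- *That none of the analysed outcomes is a declared endpoint.* Mortality is the declared endpoint death.
- *That the plan restricts the comparison to admitted patients and so is biased.* That is the literal reading of two undefined outcomes, not a stated rule. The documents support a possible bias, not an established one.
- *That the power figures measure the harm.* They rest on assumed hazard ratios and event proportions, and do not address selection.

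The mismatch itself stands. Even on the loosest reading, exacerbations managed without admission and hospitalizations for other causes have no described analysis, and stay length remains undeclared. The charitable readings are also choices that the plan does not make.

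**Conclusion.** The concern holds in a limited form. The two sections conflict: one of three declared secondary endpoints is analysed as declared, and two of three analysed outcomes are undeclared, depend on admission as worded, and have no stated population or time origin. This rests on the text alone and needs no assumed figure.

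Bias from conditioning on an admission after baseline is a risk under the literal reading, and its size cannot be estimated from the documents. The loss of power is illustrative only. These are secondary endpoints, so the primary objective is not affected, but they carry the study's prognostic claim. The change should be made before outcome data are analysed.

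**What to change.** Replace the outcome sentence in the prognostic section so that the declared endpoints are analysed from the baseline visit over 2 years, in all enrolled patients of the compared groups:

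- time to first acute exacerbation, with death as a competing event;
- time to first hospitalization, with death as a competing event;
- time to death.

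State whether the endpoint list is a composite or three separate endpoints. Replace readmission with admission for exacerbation counted from baseline. Report hospital days per patient-year, zero for those never admitted, descriptively in place of stay length. If the sponsor prefers to keep stay length and readmission, the alternative is to declare them as endpoints with a defined population and time origin; the declared endpoints would still need their own analysis or have to be withdrawn openly.

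The cost is mostly wording, but not only that. The documents give contact times at 6, 12 and 24 months; they do not define an exacerbation or say that the dates of exacerbations managed without admission are recorded. The sponsor must supply the definition and confirm that dates are captured, which may mean a small change to data collection. Competing-event handling goes beyond the stated Kaplan-Meier and log-rank methods and adds a little analysis work.

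### The acute exacerbation readmission rate is analysed only by Kaplan-Meier and log-rank, which in standard form uses first events, estimates no rate per patient-year and ignores repeat events

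*Combined protocol and SAP*

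**What the plan says.** Under Follow-up Endpoints the protocol lists "Acute exacerbations, hospitalizations, or death within 2 years" as secondary, with visits at 6, 12 and 24 months. The section on the prognostic predictive value of sarcopenic obesity names three outcomes: length of hospital stay, readmission for exacerbation (called a rate) and mortality. After length of stay, its text reads "acute exacerbation readmission rate, and mortality between COPD patients with sarcopenic obesity and those without sarcopenia at baseline were compared". One method is given for all three: "Kaplan-Meier analysis was used for statistical analysis, and differences were expressed using the log-rank test".

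The documents do not define the rate. They give no person-time denominator, no rule for repeat events and no count or recurrent-event model. The Sample Size Calculation rests on repeated-measures ANOVA and states no power or event number for readmission.

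**The concern.** Exacerbations and admissions can recur in the same patient over 2 years; death cannot. A log-rank comparison of time to first readmission counts a patient admitted once the same as a patient admitted five times. If the rate is meant as events over time, the planned method does not estimate the outcome it is attached to. This section is where the study tests prognostic value, which is its stated purpose, and the burden of repeat admissions would be left out of that test. Where readmission is frequent, the ignored events also carry information that a group of 33 can ill afford to lose.

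**Working it through.** **Inputs from the documents.** The Sample Size Calculation lists "33 sarcopenic obese, 33 non-obese sarcopenic, 72 obese non-sarcopenic, and 72 non-obese non-sarcopenic". Patients without sarcopenia number 72 + 72 = 144, so the comparison is 33 against 144 (177 patients) over T = 2 years. Alpha is 0.05, taken here as two-sided.

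**The plan's own figure.** The plan says "the study requires 200 participants", but the four groups sum to 33 + 33 + 72 + 72 = 210. The ANOVA size cannot be recomputed, because effect size, SD, within-patient correlation and number of measurements are not given. That mismatch is a separate matter and does not affect this point.

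**Assumptions, none from the documents.** Control rate r0 of 0.1 to 1.2 events per year, rate ratio (RR) 1.5 or 2.0, gamma dispersion k, no deaths and no dropout.

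**Formulas.** Expected events per patient are μ0 = r0·T and μ1 = RR·r0·T.
- Patients with at least one event: n·[1 − (1 + kμ)^(−1/k)].
- All-event (negative binomial) power: Φ(ln RR / SE − 1.96), with SE² = (1/μ0 + k)/144 + (1/μ1 + k)/33.
- First-event log-rank power: simulation with gamma frailty, 4,000 runs per scenario.

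**One case in full** (r0 = 0.4, RR 1.5, k = 1), so μ0 = 0.8 and μ1 = 1.2.
- First events: 144 × (1 − 1/1.8) = 64 and 33 × (1 − 1/2.2) = 18, together 82.
- All events: 144 × 0.8 + 33 × 1.2 = 115.2 + 39.6 = 154.8. Share ignored: 1 − 82/154.8 = 47%.
- SE² = 2.25/144 + 1.833/33 = 0.0156 + 0.0556 = 0.0712, so SE = 0.267. Power = Φ(0.405/0.267 − 1.96) = Φ(−0.44) = 33%.
- Log-rank power by simulation: 23%.

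**Results for k = 0.7 to 1.0**

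| RR | Control rate per year | First events / all events | Share ignored | Log-rank power | All-event power | Gain (points) |
|---|---|---|---|---|---|---|
| 1.5 | 0.1 | 32–33 / 39 | 16–18% | 16–19% | 16–17% | none |
| 1.5 | 0.2 | 53–56 / 77 | 28–31% | 21–23% | 24–26% | 3–4 |
| 1.5 | 0.4 | 82–87 / 155 | 44–47% | 23–26% | 33–38% | 10–12 |
| 1.5 | 0.8 | 112–120 / 310 | 61–64% | 24–28% | 41–50% | 18–22 |
| 1.5 | 1.2 | 128–136 / 464 | 71–73% | 24–29% | 45–56% | 21–27 |
| 2.0 | 0.1 | 33–34 / 42 | 18–20% | 39–43% | 44–47% | 4–5 |
| 2.0 | 0.2 | 56–58 / 84 | 31–34% | 47–53% | 63–68% | 15–16 |
| 2.0 | 0.4 | 84–89 / 168 | 47–50% | 55–59% | 78–85% | 22–26 |
| 2.0 | 0.8 | 114–122 / 336 | 64–66% | 54–62% | 87–94% | 31–33 |
| 2.0 | 1.2 | 129–138 / 504 | 73–74% | 52–63% | 90–96% | 33–37 |

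Over the wider range k = 0.3 to 2.5 the gain still runs from about 0 to 37 points.

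**Check on the formula.** The all-event power is a large-sample approximation. At RR 1.7, 0.5 per year and k = 0.5 to 1.0 it gives 57–72%. Simulating the fitted model gave 55–69%, so the formula is 2 to 3 points optimistic there. With no true effect, the simulated error rate was 4.4–4.9% for log-rank and 5.4–5.8% for negative binomial.

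**Limit set by the small group.** With p = 33/177, the first events needed for 90% power are (1.96 + 1.2816)² / [p(1 − p)(ln HR)²]. At HR 1.5 this is 10.51/(0.1517 × 0.1644), or 422, more than the 177 patients compared. At HR 2.0 it is 145. All-event analysis also stays short of 90% at RR 1.5: the highest value with overdispersion was 77% (1.2 per year, k = 0.3).

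**The case against.** The strongest reply is that the rate may simply mean the proportion readmitted. It stands beside mortality, and the endpoint can be read as whether an event occurred within 2 years. On that reading a first-event analysis is coherent and log-rank is a valid test with its error rate under control. This stands in part: the documents do not settle the meaning, so a reader should not infer that the method is plainly wrong for the outcome. Even on that reading, the plan needs a definition and still says nothing about repeat events.

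A reader might also infer that the method loses much of the available power, or that a true excess would be missed because of it. The documents do not support either, because they give no event rate, dispersion or effect size. At 0.1 events per year and RR 1.5 nothing is gained. At 0.2 per year and RR 1.5 both methods have only 21–26% power, so the small group is the main limit there. The endpoint is secondary and no power is claimed for it.

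A third inference, that only analysis wording needs to change, fails too. The data list includes exacerbations in the past year, but it does not specify full event counts or time at risk during follow-up.

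Finally, the calculation ignores deaths, dropout and confounding. The groups are not randomised, and a more precise comparison does not remove confounding.

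**Conclusion.** The concern holds in a limited form. The only method named for the readmission rate uses, in standard form, each patient's first event. It does not estimate events per patient-year, and nothing else in the plan uses repeat events. That part rests on the text alone.

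The power cost is conditional. For 33 against 144 patients and k of 0.7 to 1.0, the gain from using all events is nil at 0.1 per year with RR 1.5 and 4 to 5 points with RR 2.0. It is 3 to 16 points at 0.2 per year and 10 to 37 points at 0.4 to 1.2 per year. All rates, rate ratios and dispersions are assumed. This is a cheap improvement to a secondary analysis; it does not invalidate the log-rank test.

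**What to change.** - Define the readmission outcome as the number of events per patient-year.
- Record every exacerbation and every COPD admission, with time at risk, at the 6, 12 and 24 month follow-ups. State that time at risk ends at death or last contact.
- Compare groups by negative binomial regression with log(time at risk) as offset. Report the rate ratio with a 95% CI, robust or bootstrap given 33 patients.
- Fit a second model adjusted for the past-year exacerbation count, which is already collected.
- Keep Kaplan-Meier and log-rank for mortality and, as a supportive display, for time to first readmission.

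The cost is a line of event-recording text, a revised analysis paragraph and a slightly liberal test (about 5–6%) in a small group, which the robust or bootstrap interval is meant to address. No extra patients or visits are needed.

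### The title promises a phase-angle prognostic model, but no planned analysis relates phase angle to exacerbation, hospitalisation or death, and the only event analysis is an unadjusted log-rank with an unreconciled comparator

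*Combined protocol and SAP*

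**What the plan says.** The title announces a prognostic model for COPD with sarcopenic obesity built on bioelectrical impedance phase angle. The Research Objectives include the role of phase angle in predicting adverse outcomes. Follow-up Endpoints lists exacerbation, hospitalisation or death within two years as secondary endpoints.

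In the analysis text, phase angle appears in two places:

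- In the section on demographic characteristics and clinical data, it is one of the variables compared between groups by t-test. The grouping is "Based on whether the patients had sarcopenic obesity, they were divided into two groups"; the statistical paragraph after Follow-up Endpoints uses the same split: "Grouping patients based on whether they have sarcopenic obesity, the differences in clinical data between the two groups were analyzed".
- In the section on associated factors, the predictor list ends "whole-body and segmental phase angle, logistic regression was applied to analyze the factors associated with sarcopenic obesity in COPD patients".

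The section on prognostic predictive value covers length of hospital stay, readmission for exacerbation and death. It states that "mortality between COPD patients with sarcopenic obesity and those without sarcopenia at baseline were compared" and gives the method as "Kaplan-Meier analysis was used for statistical analysis, and differences were expressed using the log-rank test". It names no covariate, regression model or phase-angle term, and no measure of discrimination or calibration.

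Under Assessments, phase angle is "Measured via InBody S10 at six frequencies (1kHz–1000kHz) across five body segments". The formula that follows fixes the segments for the whole-body value (right arm, trunk, right leg) but names no frequency.

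**The concern.** There are three linked problems.

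1. **The headline question has no analysis.** A logistic model for sarcopenic-obesity status says whether phase angle marks body composition at baseline. It says nothing about who later exacerbates, is hospitalised or dies. With the frequency left open, any phase-angle analysis added later could also be chosen after seeing the data.
2. **The only event analysis is unadjusted.** The groups are observational and defined by body composition, so they may differ in age, sex and disease severity. The plan collects age and sex, "comorbidities (Charlson Comorbidity Index"), and "pulmonary function tests, COPD exacerbations in the past year, CAT score, mMRC score", but uses none of them here.
3. **The comparator is not reconciled.** Elsewhere patients are split by sarcopenic obesity yes or no. The outcome analysis compares sarcopenic obesity with absence of sarcopenia. This may be deliberate, but the text does not say so.

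A significant log-rank result could therefore reflect age, sex, lung function or sarcopenia alone, and might still be reported under a title about phase angle.

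**Working it through.** **Where phase angle is used**

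| Section | Role of phase angle | Outcome |
|---|---|---|
| Demographic characteristics and clinical data | variable compared by t-test | none |
| Associated factors | candidate predictor | sarcopenic-obesity status |
| Prognostic predictive value | absent | stay length, readmission, death |

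Analyses with phase angle as predictor and an event as outcome: 0.

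**Who is compared.** Sample Size Calculation lists 33 sarcopenic obese, 33 non-obese sarcopenic, 72 obese non-sarcopenic and 72 non-obese non-sarcopenic. These sum to 210, not the stated 200; I use 210 and give 200 where it matters.

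- Comparator as worded: 33 vs 72 + 72 = 144, total 177. Omitted: 33/210 = 15.7%.
- Yes/no split: 33 vs 33 + 144 = 177, total 210.

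The choice hardly moves power. By the Schoenfeld formula, at an assumed hazard ratio (HR) of 2.0, 30% events and two-sided 5%, power is 0.50 for 33 vs 144 and 0.52 for 33 vs 177. What changes is the meaning of the result.

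**What the data could support.** The documents give no event rate. I assume 10–30% over two years and use 10 events per parameter as a rule of thumb.

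- 210 × 0.10 to 0.30 = 21 to 63 events, about 2 to 6 parameters.
- Five parameters: 50 events = 23.8% of 210, 25.0% of 200, 28.2% of 177.
- Six parameters: 60 events = 28.6% of 210.
- A model built only in the 33 sarcopenic-obese patients, one reading of the title: 3.3 to 9.9 events, at most one parameter.

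**Precision for phase angle.** The 95% CI is the HR per SD multiplied or divided by exp(1.96/√(D·v)). D is the number of events and v the share of phase-angle variance not explained by the covariates (0.7 is an assumption).

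| D | v = 1 | v = 0.7 |
|---|---|---|
| 21 | 1.53 | 1.67 |
| 50 | 1.32 | 1.39 |
| 63 | 1.28 | 1.34 |

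Simulated five-parameter Cox fits (210 patients, v = 0.7, 200 runs each) gave 1.41 at about 50 events and 1.35 at about 64, so the formula is slightly optimistic. At 50 events and v = 0.7, the HR per SD detectable with 80% power is exp(2.80/√35) = 1.61.

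**Precision for the adjusted sarcopenic-obesity contrast.** With 33 vs 144, p = 33/177 = 0.186 and p(1 − p) = 0.152. At 50 events, SE = 1/√(50 × 0.152) = 0.363 and the CI factor is 2.04, or 2.34 with v = 0.7. If events spread in proportion to group size, only about 9 fall in the sarcopenic-obese group.

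**Can sarcopenic obesity be separated from sarcopenia plus obesity?** That needs a sarcopenia-by-obesity interaction. SE = √(Σ 1/d) over the four groups, with events d proportional to group size. The detectable ratio of HRs is exp(2.802·SE) at 80% power and exp(3.242·SE) at the protocol's 90%.

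- 21 events (3.3, 3.3, 7.2, 7.2): SE 0.940; ratios 13.9 and 21.1.
- 63 events (9.9, 9.9, 21.6, 21.6): SE 0.543; ratios 4.6 and 5.8.
- 105 events (50% of 210): SE 0.420; ratios 3.2 and 3.9.

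It is untestable in practice throughout.

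**The case against.** **An unadjusted contrast is legitimate.** Under a prognostic heading, a crude comparison of baseline groups is a valid description, and that section does not expressly claim independent value. This stands as far as it goes. It does not supply the phase-angle analysis, and a crude difference cannot be attributed to sarcopenic obesity.

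**The yes/no split does not isolate sarcopenic obesity either.** This is correct: it only mixes the 33 non-obese sarcopenic patients into the reference group. The limitation applies to both comparators, so the request is to state one, show all four groups and claim no more than the contrast supports.

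**The event range is arbitrary.** It is an assumption, and the secondary endpoint counts any acute exacerbation, which could be more frequent. At 50%, 210 patients give 105 events, enough for ten parameters by the same rule. Modelling would then be easier, but the missing analysis would still be missing.

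**The clinical-data comparison might cover events.** Even read that way, it compares patients by sarcopenic-obesity status, unadjusted, and does not relate phase angle to outcome.

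**The remedy fits the aims imperfectly.** The objectives speak of multi-segment phase angle, and one whole-body term makes the segmental values exploratory. The title can also be read as a model within sarcopenic-obese patients only. Both points are fair and should be settled in the text; with at most about 10 events in those 33 patients under the assumed rates, the narrower reading is not workable.

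**Selection.** The exclusion criteria remove patients with incomplete follow-up, withdrawal or loss to follow-up. A whole-cohort Cox model inherits that selection, as does the log-rank already planned.

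**Conclusion.** The concern holds, with high confidence. The core rests on the text, not on a calculation: no planned analysis relates phase angle to an event, although the title and objectives promise one. The unadjusted log-rank is a weaker substitute, and its comparator needs one clarifying sentence; on the listed sizes, 33 of 210 patients (15.7%) are in or out depending on the reading.

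A five-parameter phase-angle model is feasible at about 50 events, with a 95% CI of the HR per SD multiplied or divided by about 1.3 to 1.4. The adjusted sarcopenic-obesity contrast is much less precise, by a factor of about 2.0 to 2.3. The event rates, the 30% variance explained by covariates and the 10-events rule are assumptions. This is an inexpensive improvement to the plan.

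**What to change.** 1. **Phase-angle model.** Pre-specify a Cox model in the whole cohort for one defined event outcome, for example time to first exacerbation hospitalisation or death. Enter baseline whole-body phase angle at one named frequency as a single continuous term, with age, sex, FEV1 % predicted and prior-year exacerbations (five parameters, about 50 events). Sex belongs because the body-composition cut-offs are sex-specific. Report the HR per SD with its CI, and the optimism-corrected change in C-index over the covariates alone. If events are fewer, drop covariates in a pre-stated order or use penalised estimation. A sixth term (Charlson index, or sarcopenic-obesity status to see whether phase angle adds to it) needs about 60 events. Say in the objectives that the model is for the whole cohort.
2. **Group comparison.** State one comparator and why, and show Kaplan-Meier curves for all four baseline groups. Support the log-rank with a Cox model adjusted for the same four covariates (about 50 events, 28% of 177 if the present comparator is kept). Report its expected width, and state that the interaction cannot in practice be tested, so the result is a prognostic contrast and not evidence of an effect beyond sarcopenia plus obesity.

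**Cost.** SAP wording and two extra models; no new measurement. Event dates are not in the data-collection list and should be confirmed, though the log-rank already needs them. Adjusted intervals may be wider than unadjusted ones. Software other than SPSS 24.0 may be needed for the C-index correction or penalised fitting. The other frequencies and the segmental values become exploratory.
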